5.1. Inclusion Criteria

Participants are eligible to be included in the study only if all of the following criteria apply:

- 1. Ability to comprehend and willingness to sign a written ICF for the study.
- 2. Men and women 18 years of age or older (or as applicable per local country requirements).
- 3. Confirmed diagnosis of one of the following:
 - a. Treatment-naive metastatic NSCLC with high PD-L1 expression (TPS \geq 50%) and no EGFR, ALK, or ROS activating genomic tumor aberrations.
 - b. Locally-advanced or metastatic UC in participants who are not eligible for cisplatin therapy (determined by the investigator) and whose tumors express PD-L1 with a CPS ≥ 10 .
 - c. Unresectable or metastatic melanoma.
 - d. Locally advanced or metastatic RCC with clear cell component (with or without sarcomatoid features) and having received no prior systemic therapy
- 4. Measurable disease per RECIST v1.1.
- 5. ECOG performance status 0 to 1.
- 6. Willingness to avoid pregnancy or fathering children based on the criteria below.
 - a. Men must agree to take appropriate precautions to avoid fathering children (with at least 99% certainty) from screening through 6 months after the last dose of study drug (or longer as appropriate based on country-specific requirements) and must refrain from donating sperm during this period. Permitted methods that are at least 99% effective in preventing pregnancy (see Appendix A) should be communicated to the participants and their understanding confirmed.
 - b. Women of childbearing potential must have a negative serum pregnancy test at screening and must agree to take appropriate precautions to avoid pregnancy (with at least 99% certainty) from screening through 6 months after the last dose of study drug. Permitted methods that are at least 99% effective in preventing pregnancy (see Appendix A) should be communicated to the participants and their understanding confirmed.
 - c. Women of nonchildbearing potential (ie, surgically sterile with a hysterectomy and/or bilateral oophorectomy $OR \ge 12$ months of amenorrhea and at least 50 years of age) are eligible.

5.2. Exclusion Criteria

Participants are excluded from the study if any of the following criteria apply:

- 1. Receipt of anticancer therapy or participation in another interventional clinical study within 21 days before the first administration of study drug.
- 2. Prior treatment with PD-1 or PD-L1 directed therapy (other immunotherapies may be acceptable with prior approval from the medical monitor).
 - a. Adjuvant therapy that was completed ≥ 12 months before study entry may be acceptable but should be discussed with the medical monitor before enrolling the participant on study.
- 3. Radiotherapy within 14 days of first dose of study treatment with the following caveats:
 - a. 28 days for pelvic radiotherapy.
 - b. 6 months for thoracic region radiotherapy that is > 30 Gy.
 - c. 14 days for palliative radiation therapy. Note: Participants must have recovered from all radiation-related toxicities, not require corticosteroids for this purpose, and not have had radiation pneumonitis.
- 4. Toxicity of prior therapy that has not recovered to ≤ Grade 1 or baseline (with the exception of anemia not requiring transfusion support and any grade of alopecia). Endocrinopathy, if well-managed, is not exclusionary and should be discussed with sponsor medical monitor.
- 5. Participant has not recovered adequately from toxicities and/or complications from surgical intervention before starting study drug.
- 6. Participants with laboratory values at screening defined in Table 7.

Laboratory Parameter		Exclusion Criterion
Her	natology	
а	Platelets	$\leq 100 \times 10^{9}/L$
b	Hemoglobin	$\leq 9 \text{ g/dL}$
с	ANC	$\leq 1.5 \times 10^{9}/L$
Hep	patic	
d	ALT	> 2.5 × ULN
e	AST	> 2.5 × ULN
f	Bilirubin	\geq 1.5 × ULN unless conjugated bilirubin \leq ULN (conjugated bilirubin only needs to be tested if total bilirubin exceeds ULN). If there is no institutional ULN, then direct bilirubin must be < 40% of total bilirubin.
Ren	al	
g	Calculated creatinine clearance	< 30 mL/min
Coa	gulation	
h	INR or PT	$> 1.5 \times ULN$ for participants not receiving anticoagulant therapy
i	aPTT	$> 1.5 \times ULN$ for participants not receiving anticoagulant therapy

Table 7:Exclusionary Laboratory Values

- 7. Known additional malignancy that is progressing or requires active treatment, or history of other malignancy within 3 years of study entry with the exception of cured basal cell or squamous cell carcinoma of the skin, superficial bladder cancer, prostate intraepithelial neoplasm, carcinoma in situ of the cervix, or other noninvasive or indolent malignancy, or cancers from which the participant has been disease-free for > 1 year, after treatment with curative intent.
- 8. Active autoimmune disease requiring systemic immunosuppression in excess of physiologic maintenance doses of corticosteroids (> 10 mg of prednisone or equivalent).
 - a. Physiologic corticosteroid replacement therapy at doses > 10 mg/day of prednisone or equivalent for adrenal or pituitary insufficiency and in the absence of active autoimmune disease is permitted.
 - b. Participants with asthma that requires intermittent use of bronchodilators, inhaled steroids, or local steroid injections may participate.
 - c. Participants using topical, ocular, intra-articular, or intranasal steroids (with minimal systemic absorption) may participate.
 - d. Brief courses of corticosteroids for prophylaxis (eg, contrast dye allergy) or study treatment–related standard premedication are permitted.
- 9. Evidence of interstitial lung disease or active noninfectious pneumonitis.
- 10. Known active CNS metastases and/or carcinomatous meningitis.

Note: Participants with previously treated brain metastases may participate provided they are stable (without evidence of progression by imaging for at least 28 days before the first dose of study drug and any neurologic symptoms have returned to baseline), have no evidence of new or enlarging brain metastases or CNS edema, and have not required steroids for at least 14 days before the first dose of study drug.

- 11. Known active HAV, HBV, or HCV infection, as defined by elevated transaminases with the following serology: positivity for HAV IgM antibody, anti-HCV, anti-HBc IgG or IgM, or HBsAg (in the absence of prior immunization).
- 12. Active infections requiring systemic therapy.

- 14. Known hypersensitivity to another mAb that cannot be controlled with standard measures (eg, antihistamines and corticosteroids).
- 15. Participants with impaired cardiac function or clinically significant cardiac disease:
 - a. New York Heart Association Class III or IV cardiac disease, including preexisting clinically significant ventricular arrhythmia, congestive heart failure, or cardiomyopathy.
 - b. Unstable angina pectoris.
 - c. Acute myocardial infarction ≤ 6 months before study participation.
 - d. Other clinically significant heart disease (eg, \geq Grade 3 uncontrolled hypertension).

CONFIDENTIAL

- 16. Participant is pregnant or breastfeeding.
- 17. Has received a live vaccine within 28 days of the planned start of study drug.

Note: Examples of live vaccines include, but are not limited to, the following: measles, mumps, rubella, chicken pox/zoster, yellow fever, rabies, BCG, and typhoid vaccine. Seasonal influenza vaccines for injection are generally killed virus vaccines and are allowed; however, intranasal influenza vaccines (eg, FluMist[®]) are live-attenuated vaccines and are not allowed.

- 18. Current use of prohibited medication as described in Section 6.6.2.
- 19. Any condition that would, in the investigator's judgment, interfere with full participation in the study, including administration of study drug and attending required study visits; pose a significant risk to the participant; or interfere with interpretation of study data.
- 20. History of organ transplant, including allogeneic stem cell transplantation.
- 21. The following patients are excluded in France: vulnerable populations according to article L.1121-6 of the French Public Health code and adults under legal protection or who are unable to express their consent per article L.1121-8 of the French Public Health code.

5.3. Lifestyle Considerations

Not applicable.

5.4. Screen Failures

Screen failures are defined as participants who consent to participate in the clinical study but are not subsequently assigned to study drug.

Tests with results that fail eligibility requirements may be repeated during screening. Additionally, a participant who fails screening may repeat the screening process once if the investigator believes that there has been a change in eligibility status. Participants who rescreen must reconsent and be assigned a new participant number.

5.5. Replacement of Participants

Not applicable.

6. STUDY TREATMENT

6.1. Study Treatments Administered

Table 8 presents the study drug information.

Table 8:	Study Drug Information
----------	------------------------

Study drug name:	INCMGA00012
Dosage formulation:	Liquid formulation
Dosage level:	500 mg Q4W
Route of administration:	IV
Administration instructions:	Administered intravenously over 30 minutes (- 5/+ 15 minutes)
Packaging and labeling:	INCMGA00012 25 mg/mL will be provided in a glass vial for single use Each vial will be labeled as required per country requirement
Storage:	Upright under refrigeration at 2°C-8°C (36°F-46°F) Protected from light

6.2. Preparation, Handling, and Accountability

The investigator or designee must confirm appropriate temperature conditions have been maintained during transit for all study drug received and any discrepancies are reported and resolved before use of the study drug.

Only participants enrolled in the study may receive study drug, and only authorized site staff may supply or administer study drug. All study drug must be stored in a secure, environmentally controlled, and monitored (manual or automated) area in accordance with the labeled storage conditions with access limited to the investigator and authorized site staff.

The investigator (or designee) is responsible for study drug accountability, reconciliation, and record maintenance (ie, receipt, reconciliation, and final disposition records). Inventory and accountability records must be maintained and readily available for inspection by the study monitor and are open to inspection at any time by any applicable regulatory authorities. The investigator or designee must maintain records that document:

- Delivery of study drug to the study site.
- Inventory of study drug at the site.
- Lot numbers and/or vial numbers (as applicable) of study drug used to prepare the infusion solution.
- Return of study drug to the investigator or designee by participants.

The investigational product must be used only in accordance with the Protocol. The investigator will also maintain records adequately documenting that the participants were provided the specified study drug. These records should include dates, quantities, and any available batch or

serial numbers or unique code numbers assigned to the investigational product and study participants.

Completed accountability records will be archived by the site. The investigator or designee will be expected to collect and retain all used, unused, and partially used containers of study drug until verified by the study monitor (unless otherwise agreed to by the sponsor). At the conclusion of the study, the investigator or designee will oversee shipment of any remaining study drug back to the sponsor or its designee for destruction according to institutional SOPs. If local procedures mandate on-site destruction of investigational supply, the site should (where local procedures allow) maintain the investigational supply until the study monitor inspects the accountability records in order to evaluate compliance and accuracy of accountability by the investigative site. At sites where the study drug is destroyed before monitor inspection, the monitors rely on documentation of destruction per the site SOP.

Further guidance and information for the final disposition of unused study drug are provided in the Pharmacy Manual.

6.3. Measures to Minimize Bias: Randomization and Blinding

Not applicable.

6.4. Study Treatment Compliance

Compliance with all study-related treatments should be emphasized to the participant by the site personnel, and appropriate steps should be taken to optimize compliance during the study. Compliance with study drug will be calculated by the sponsor based on the drug accountability documented by the site staff and monitored by the sponsor/designee.

6.5. Dose Modifications

Dose reduction is not allowed. Before the start of each treatment cycle, the participant must meet the treatment continuation criteria (see Section 4.1). Management guidelines for immune-related adverse reactions commonly observed with other PD-1 inhibitors are provided in the following sections.

6.5.1. Management of Suspected Infusion Reactions

Infusion or hypersensitivity reactions may be observed with administration of any foreign protein. Premedication with an antipyretic (eg, acetaminophen/paracetamol) and a histamine blocker (eg, diphenhydramine) should be considered for participants who have had previous systemic reactions to protein product infusions or when recommended by institutional policy. Guidelines for management of suspected infusion reactions are provided in Table 9. Grade 3 or 4 infusion reactions should be reported within 24 hours to the study medical monitor regardless of whether criteria for reporting as an SAE are met.

Grade	Description ^a	Treatment	Subsequent Infusions
1	Mild reaction; interrupt or slow the rate of infusion; intervention not indicated.	Monitor vital signs closely until medically stable.	Premedication with an antipyretic (eg, acetaminophen/ paracetamol) and a histamine blocker (eg, diphenhydramine) should be considered for participants who have had previous systemic reactions to protein product infusions or when recommended by institutional policy.
2	Requires infusion interruption but responds promptly to symptomatic treatment (eg, antihistamines, NSAIDs, narcotics, IV fluids); prophylactic medications indicated for ≤ 24 hours.	First occurrence: Stop infusion and initiate appropriate medical measures (eg, IV fluids, antihistamines NSAIDs, antipyretic, narcotics, per institutional preferences). Monitor vital signs until medically stable. If symptoms resolve within 1 hour, infusion may be resumed at 50% of the original infusion rate. Subsequent occurrences (after recommended prophylaxis): Permanently discontinue treatment.	Premedicate at least 30 minutes before infusion with antihistamines (eg, diphenhydramine 50 mg PO) and antipyretic (eg, acetaminophen/ paracetamol 500-1000 mg PO). Additional supportive measures may be acceptable (per institutional preference). Next infusion should start at 50% of the original infusion rate. If no reaction, rate of infusion can be increased by 25% every 15 minutes until a rate of 100% has been reached. Subsequent infusions can begin at 100%.
3 or 4	Grade 3: Prolonged (ie, not rapidly responsive to symptomatic medication and/or brief interruption of infusion); recurrence of symptoms following initial improvement; hospitalization indicated for other clinical sequelae (eg, renal impairment, pulmonary infiltrates). Grade 4: Life-threatening; pressor or ventilatory support indicated.	Stop infusion and initiate appropriate medical therapy (eg, IV fluids, antihistamines NSAIDs, antipyretic, narcotics, oxygen, pressors, epinephrine, corticosteroids, per institutional preferences). Monitor vital signs frequently until medically stable. Hospitalization may be indicated.	Discontinue study drug.

Table 9: Guidelines for Management of Suspected Infusion Reaction

^a Per NCI CTCAE v5.0, appropriate resuscitation equipment should be available at the bedside and a physician readily available during the period of study drug administration.

6.5.2. Management of Suspected Immune-Related Adverse Events

Adverse events of a potential immunologic etiology or irAEs may be defined as an AE of unknown etiology, associated with drug exposure, and consistent with an immune phenomenon. Immune-related AEs may be predicted based on the nature of the compounds, their mechanism of action, and reported experience with immunotherapies that have a similar mechanism of action. Special attention should be paid to AEs that may be suggestive of potential irAEs. An irAE can occur shortly after the first dose or several months after the last dose of treatment.

If an irAE is suspected, efforts should be made to rule out neoplastic, infectious, metabolic, toxin, or other etiologic causes before labeling an AE as an irAE. Recommendations for management of specific immune-mediated AEs known to be associated with INCMGA00012 and other PD-1 inhibitors (eg, pembrolizumab, nivolumab) are provided in Table 10.

Management guidance for irAEs not detailed elsewhere in the Protocol should follow the ASCO or ESMO Clinical Practice Guidelines (Brahmer et al 2018, Haanen et al 2017, Haanen et al 2018, NCCN 2021).

Immune-Related Adverse Event	Toxicity Grade or Conditions (CTCAE v5.0)	Action Taken With INCMGA00012	AE Management With Corticosteroid and/or Other Supportive Care Therapies	
Pneumonitis	Grade 1	No action.	None.	
	Grade 2	Withhold until ≤ Grade 1.	• Administer systemic corticosteroids per local practice followed by taper.	
	Grades 3 or 4, or recurrent Grade 2	Permanently discontinue.	• Evaluate participants with suspected pneumonitis with radiographic imaging and initiate corticosteroid treatment.	
			• Add prophylactic antibiotics for opportunistic infections.	
Diarrhea/colitis	Grade 1	No action.	None.	
	Grades 2 or 3	Withhold until ≤ Grade 1.	 Consider prompt initiation of standard antidiarrheal agents and other necessary 	
	Grade 4 or recurrent Grade 3	Permanently discontinue.	supportive care as needed (eg, oral and/or IV fluids).	
			 Administer systemic corticosteroids per local practice followed by taper. 	
			 Consider prophylactic antibiotics per local practice. 	
			• Consider gastrointestinal consultation and performing endoscopy to rule out colitis.	

Table 10:Dose Modification and Toxicity Management Guidelines for
Immune-Related Adverse Events

Immune-Related	Toxicity Grade or Conditions	Action Taken With	AE Management With Corticosteroid and/or
Adverse Event	(CTCAE v5.0)	INCMGA00012	Other Supportive Care Therapies
Hepatitis with no tumor involvement of the liver ^a	AST or ALT increases to more than 3 and up to 8 times ULN or Total bilirubin increases to more than 1.5 and up to 3 times ULN AST or ALT increases to more than 8 times ULN or Total bilirubin increases	Withhold. Permanently discontinue.	 Administer systemic corticosteroids per local practice followed by taper. Consider monitoring liver enzymes weekly (or more frequently) until liver enzyme value returns to baseline or is stable.
	to more than 3 times		
Hepatitis with tumor involvement of the liver	Baseline AST or ALT is more than 1 and up to 3 times ULN and increases to more than 5 and up to 10 times ULN or Baseline AST or ALT is more than 3 and up to 5 times ULN and increases to more than 8 and up to 10 times ULN	Withhold.	 Administer systemic corticosteroids per local practice followed by taper. Consider monitoring liver enzymes weekly (or more frequently) until liver enzyme value returns to baseline or is stable.
	ALT or AST increases to more than 10 times ULN or Total bilirubin increases to more than 3 times ULN	Permanently discontinue.	
Endocrinopathies	Grades 1 and 2	No action.	None.
 Type 1 diabetes mellitus Hyperglycemia	Grades 3 or 4 Type 1 diabetes mellitus (or hyperglycemia)	Withhold until \leq Grade 1 or is otherwise clinically stable.	Initiate treatment with antihyperglycemics as clinically indicated.
 Hyperthyroidism Hypothyroidism Adrenal insufficiency 	Grades 3 and 4 hyperthyroidism	Withhold until \leq Grade 1 or is otherwise clinically stable.	Initiate symptomatic management.
	Grades 3 and 4 hypothyroidism	Withhold until \leq Grade 1 or is otherwise clinically stable.	Initiate thyroid replacement hormones (eg, levothyroxine or liothyronine) per standard of care.
	Grade 2 adrenal insufficiency	Withhold until \leq Grade 1 or otherwise clinically stable.	Initiate treatment with hormone replacement as clinically indicated.
	Grades 3 and 4 adrenal insufficiency	Withhold until \leq Grade 1 after corticosteroid taper to \leq 10 mg/day prednisone or equivalent or is otherwise clinically stable.	Initial dose of 1 to 2 mg/kg/day prednisone or equivalent followed by a taper and hormone replacement as clinically indicated.

Table 10:Dose Modification and Toxicity Management Guidelines for
Immune-Related Adverse Events (Continued)

Immune-Related Adverse Event	Toxicity Grade or Conditions (CTCAE v5.0)	Action Taken With INCMGA00012	AE Management With Corticosteroid and/or Other Supportive Care Therapies
Endocrinopathies (continued)	Grade 1	No action.	None.
• Hypophysitis	Grade 2 (asymptomatic)	Withhold until ≤ Grade 1. May restart INCMGA00012 treatment after controlled by hormone replacement therapy.	Administer hormonal replacement.
	Grade 2 (symptomatic, eg, headaches, visual disturbances)	Withhold until ≤Grade 1. May restart INCMGA00012 treatment after controlled with hormone replacement, if indicated, and steroid taper is complete.	 Administer corticosteroids at initial dose of 1 to 2 mg/kg/day prednisone or equivalent followed by a taper, and initiate other hormonal replacements as clinically indicated. Consult with endocrinologist as needed.
	Grade 3 or 4 (symptomatic)	Permanent discontinuation should occur if after withholding INCMGA00012 the toxicity does not resolve to \leq Grade 1 within 12 weeks after last dose of INCMGA00012 treatment, or if corticosteroid dosing cannot be reduced to \leq 10 mg prednisone or equivalent per day within 12 weeks. Permanent discontinuation of INCMGA00012 should take place earlier at the investigator's discretion, if corticosteroids and/or hormone replacement therapy cannot balance the participant's pituitary function.	 Administer corticosteroids at initial dose of 1 to 2 mg/kg/day prednisone or equivalent followed by a taper, and initiate other hormonal replacements as clinically indicated. Consult with endocrinologist as needed.

Table 10:Dose Modification and Toxicity Management Guidelines for
Immune-Related Adverse Events (Continued)

Table 10:	Dose Modification and Toxicity Management Guidelines for		
	Immune-Related Adverse Events (Continued)		

	Immune-Related Adverse Event	Toxicity Grade or Conditions (CTCAE v5.0)	Action Taken With INCMGA00012	AE Management With Corticosteroid and/or Other Supportive Care Therapies
	Nephritis with renal	Grade 1	No action.	None.
	dysfunction	Grade 2 or Grade 3 increased blood creatinine	Withhold until \leq Grade 1.	Administer corticosteroids per local practice followed by taper.
		Grade 4 increased blood creatinine	Permanently discontinue.	
	Skin (eg, Stevens- Johnson syndrome, or toxic epidermal necrolysis)	Grade 1	No action.	None.
		Grade 2	No action.	Manage with topical steroids with or without drug interruption.
		Grade 3 ^b or persistent Grade 2 (≥ 2 weeks) or suspected Stevens-Johnson syndrome ^c	Withhold until \leq Grade 1 after corticosteroid taper to \leq 10 mg/day prednisone or equivalent	 Administer corticosteroids per local practice followed by taper. Additionally, oral antihistamines such as diphenhydramine or famotidine (per institutional preference) may be utilized as needed. Should refer to dermatology if no resolution with these measures.
		Grade 4 or confirmed Stevens-Johnson syndrome ^b or toxic epidermal necrolysis ^d	Permanently discontinue.	 Initial dose of 1 to 2 mg/kg/day prednisone or equivalent followed by a taper. Refer to dermatology consult.
	Myocarditis	Grade 2	Depending on severity of symptoms, withhold until symptoms fully resolve and management with corticosteroids is complete. Permanent discontinuation of INCMGA00012 may take place earlier at the investigator's discretion.	 Treatment with systemic corticosteroids should be initiated (initial dose of 1-2 mg/kg per day of prednisone or equivalent). Taper as appropriate. Manage cardiac symptoms according to standard of care and with guidance from cardiology. Consider cardiac MRI and myocardial biopsy for diagnosis.
		Grades 3 or 4	Permanently discontinue.	
Imj sys (eg syn aut enc my aut neu tran	Important nervous system events	Grade 2	Withhold until ≤ Grade 1.	• Neurology consultation is recommended for all neurologic irAEs ≥ Grade 2.
	(eg, Guillain-Barre syndrome, autoimmune encephalitis, myasthenia gravis, autonomic neuropathy, or transverse myelitis)	Grades 3 or 4	Permanently discontinue.	 Treatment with systemic corticosteroids should be initiated (initial dose of 1-2 mg/kg per day of prednisone or equivalent). Taper as appropriate. For Grade 2 transverse myelitis consider permanent discontinuation. Manage symptoms according to standard of care and with guidance from neurology.

Table 10:Dose Modification and Toxicity Management Guidelines for
Immune-Related Adverse Events (Continued)

Immune-Related Adverse Event	Toxicity Grade or Conditions (CTCAE v5.0)	Action Taken With INCMGA00012	AE Management With Corticosteroid and/or Other Supportive Care Therapies
All other irAEs	Grade 2 or Grade 3 based on severity and type of reaction	Withhold until ≤ Grade 1.	Based on severity of AE, administer corticosteroids.
	Recurrent Grade 3 or Persistent Grade 2 and Grade 3	Permanently discontinue.	
	Grade 4 (excluding endocrinopathies)	Permanently discontinue.	

^a If AST and ALT are less than or equal to ULN at baseline, withhold or permanently discontinue INCMGA00012 based on recommendations for hepatitis with no liver involvement.

- ^b Participants with Grade 3 rash in the absence of desquamation, with no mucosal involvement, not requiring systemic steroids, and resolving or improving to ≤ Grade 1 within 14 days do not need INCMGA00012 interrupted. Permanent discontinuation of study drug may be necessary if there is recurrence of Grade 3 after resuming study drug.
- ^c Grade 3 Stevens-Johnson syndrome is defined as skin sloughing covering < 10% BSA with associated signs (eg, erythema, purpura, epidermal detachment, mucous membrane detachment). Grade 4 Stevens-Johnson syndrome is defined as skin sloughing covering 10% to 30% BSA with associated signs (eg, erythema, purpura, epidermal detachment, mucous membrane detachment).
- ^d Toxic epidermal necrolysis is Grade 4 by definition and is defined as skin sloughing covering ≥ 30% BSA with associated symptoms (eg, erythema, purpura, epidermal detachment).

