4.2. Overall Study Duration

The study begins when the first participant signs the ICF. The end of the study is defined as the date of the last visit of the last participant in the study. The study will end when the last participant completes 90 days of safety follow-up for irAEs. No participant will be followed for longer than 27 months (ie, 2 years of study treatment followed by 90 days of observation for irAEs in the event the participant does not discontinue treatment prematurely or start a new anticancer therapy).

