6.5.3. Permanent Discontinuation of Study Drug Due to Toxicity

The occurrence of unacceptable toxicity not caused by the underlying disease will require that the study treatment be permanently discontinued. Unacceptable toxicity is defined as follows:

- Occurrence of an AE that is related to study treatment that, in the judgment of the investigator or the sponsor's medical monitor, compromises the participant's ability to continue study-specific procedures or is considered to not be in the participant's best interest.
- Persistent treatment-related AE requiring a delay of therapy for more than 12 weeks.
- Any AE defined in the dose modifications management guidelines (see Section 6.5) requiring the study treatment be discontinued.

A complete list of study treatment discontinuation reasons and procedures is found in Section 7.

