7. DISCONTINUATION OF STUDY TREATMENT AND PARTICIPANT DISCONTINUATION/WITHDRAWAL

7.1. Discontinuation of Study Drug

7.1.1. Reasons for Discontinuation

Participants **must** be withdrawn from study drug for the following reasons:

- Disease progression (see Section 4.1).
- Unacceptable toxicity as noted in Section 6.5.3.
- The participant becomes pregnant. If the female participant is no longer pregnant and meets the treatment continuation criteria within 12 weeks of the scheduled start of a cycle, study treatment may be resumed after approval has been received from the medical monitor (see Section 9.7).
- Consent is withdrawn.

Note: Consent withdrawn means that the participant has explicitly indicated that they do not want to participate in the study or be followed any longer; in this case no further data may be solicited from or collected on the participant.

- Further study treatment would be injurious to the participant's health or well-being, in the investigator's medical judgment.
- The study is terminated by the sponsor.
- The study is terminated by the local health authority, IRB, or IEC.

A participant **may** be discontinued from study drug as follows:

• If a participant is noncompliant with study procedures or study drug administration in the investigator's opinion, the sponsor should be consulted for instruction on handling the participant.

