8.8.1. Safety Follow-Up

The safety follow-up period starts once the participant discontinues study treatment. Approximately 28 days after the final dose of study drug (\pm 7 days), participants are to attend a clinical visit for a safety evaluation. During this visit, blood will be collected for safety laboratory analysis, a physical exam will be performed, and AEs and concomitant medications will be assessed according to the scheduled assessments found in Table 3. Participants will be followed for irAEs for 90 days after the last dose of study drug or until the participant begins a new anticancer therapy, whichever occurs first. If a participant is scheduled to begin a new anticancer therapy before the end of the 28-day safety follow-up period, the safety follow-up visit should be performed before the new anticancer therapy is started.

9. ADVERSE EVENTS: DEFINITIONS AND PROCEDURES FOR RECORDING, EVALUATING, FOLLOW-UP, AND REPORTING

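### Protocol Table 10 gives two opposite instructions for Grade 2 adrenal insufficiency (minor safety-wording contradiction)

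*Protocol*

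**What the plan says.** Table 10 (Protocol Section 6.5.2) is the working guidance for dosing and treatment when an immune-related event occurs. Its first endocrinopathy block covers type 1 diabetes mellitus, hyperglycemia, hyperthyroidism, hypothyroidism and adrenal insufficiency.

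- **General row (first in the block).** It covers Grades 1 and 2, names no event and makes no exception. Study drug continues unchanged and no supportive treatment is listed.
- **Specific row (later in the same block).** It is headed "Grade 2 adrenal insufficiency". Study drug is withheld until the event is at or below "Grade 1 or otherwise clinically stable". The supportive-care cell reads "Initiate treatment with hormone replacement as clinically indicated".

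Hypophysitis has its own block with separate rows by grade, including one for "Grade 2 (asymptomatic)", and there too the drug is withheld and hormones are replaced.

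**The concern.** Adrenal insufficiency is a listed member of the block, so at Grade 2 it falls literally under both rows. One row says to carry on and give nothing; the other says to hold the drug and replace hormones as needed. A reader who stops at the first row follows the less cautious instruction.

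What is at stake is participant safety at sites using the current text, not inference. The response endpoint does not depend on this row. The descriptive dose-delay summaries (SAP Sections 6.4 and 8.2.3) could shift slightly if sites read the table differently, but the documents give no basis for sizing that.

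**Working it through.** The Protocol gives no figure to reproduce here, so the check is a side-by-side reading, followed by a date calculation for how long the text could apply.

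**1. The two rows**

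| | General row | Specific row |
|---|---|---|
| Grade | 1 and 2 | 2 |
| Event | any listed endocrinopathy | adrenal insufficiency |
| Study drug | no change | withhold |
| Supportive care | nothing listed | hormone replacement as indicated |

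For the other four listed endocrinopathies, Grade 2 appears only in the general row. The overlap is therefore exactly one event at one grade.

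**2. Is it a damaged table?** Both rows are intact, each with its drug-action and management cells. The first row cannot sensibly be limited to diabetes: Grade 1 and 2 thyroid events and Grade 1 adrenal insufficiency would then have no row at all.

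**3. Does anything else in the Protocol settle it?**
- Table 10 footnotes a to d deal with hepatitis, rash, Stevens-Johnson syndrome and toxic epidermal necrolysis only.
- Section 6.5 sends the reader to Section 4.1 for continuation criteria, and Section 4.1 points back to Section 6.5 and Table 10 for toxicity delays.
- The outside guidelines named in Section 6.5.2 are for events the Protocol does not detail, so they are not the stated fallback.
- Section 6.5.3 sets criteria for permanent discontinuation, not for a temporary hold.

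**4. Which row is intended?** If the general row governed, the specific row would never apply. Grade 2 hypophysitis is handled in the same way as the specific row. The specific row is the intended one.

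**5. How long could the Amendment 5 text apply?** Inputs:
- Amendment 5 is dated 23 JUN 2021 (Appendix C).
- The last participant was enrolled in APR 2020 (Appendix C, Amendment 4 rationale).
- Enrollment is Cycle 1 Day 1 (Section 8.1.2).
- Treatment is capped at 2 years (Section 4.1).
- On follow-up: "Participants will be followed for irAEs for 90 days after the last dose of study drug", or until a new anticancer therapy starts (Section 8.8.1).

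Dosing column:
- Latest end of dosing = APR 2020 + 2 years = 01 to 30 APR 2022.
- 23 JUN 2021 to 01 APR 2022 = 282 days; to 30 APR 2022 = 282 + 29 = 311 days.
- In 28-day cycles: 282/28 = 10.1 and 311/28 = 11.1.

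Supportive-care column:
- 01 APR 2022 + 90 days = 30 JUN 2022, and 282 + 90 = 372 days.
- 30 APR 2022 + 90 days = 29 JUL 2022, and 311 + 90 = 401 days.

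Check against Section 4.2 ("No participant will be followed for longer than 27 months"): APR 2020 + 27 months = JUL 2022, which agrees.

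On 23 JUN 2021, anyone still on drug under the cap had started on or after 23 JUN 2019. Anyone still in 90-day follow-up had a last dose on or after 25 MAR 2021.

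**The case against.** The strongest reply is that only one reading makes sense. A clinician looking up this event finds a row with exactly that label, and a named event overriding a general grade row is arguably how the table works elsewhere. In the nervous system block, Grade 2 events are withheld, while a note raises permanent discontinuation for Grade 2 transverse myelitis. In the skin block, Grade 3 leads to a hold, while confirmed Stevens-Johnson syndrome, which has a Grade 3 form, leads to discontinuation.

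These parallels do not remove the contradiction. The transverse myelitis note asks only that an option be considered, and it sits in the management cell. The Stevens-Johnson row adds the condition that the diagnosis is confirmed. The endocrine pair differs only in naming an event the general row already includes, and the instructions are opposite. The table also knows how to write an exception: its last row, for Grade 4 events, excludes endocrinopathies explicitly.

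Several points on the other side do stand:
- Intent is clear and harm is unlikely.
- Judgment clauses give a backstop: Section 6.5.3 ("Occurrence of an AE that is related to study treatment that, in the judgment of the investigator" or medical monitor, makes continuing unsuitable) and Section 7.1.1 ("Further study treatment would be injurious to the" participant's health). They concern stopping the drug, however, and do not say whether to hold it temporarily or start hormones.
- The Study Procedures Manual, which holds diagnostic algorithms for these events, is not among the documents. The statement that no rule of precedence exists is therefore about the Protocol only.
- The day counts would be the same for any wording problem in Amendment 5.
- This is an internal inconsistency; nothing suggests that anyone chose to leave Grade 2 adrenal insufficiency untreated.

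**Conclusion.** The contradiction is real and is in the current text. It is minor: one event, one grade, both instruction columns, with the error pointing in the unsafe direction. It should be corrected because the correction costs almost nothing.

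The number of participants affected cannot be estimated. The only immune-related event rate in the documents is 12%, for all types together, in another study using other doses and schedules (Protocol Section 2.1.1), and it does not size this event.

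The windows of 282 to 311 days (dosing) and 372 to 401 days (management) are upper limits on the life of the Amendment 5 text. They assume that the amendment was in force at sites on its date and that a participant enrolled in APR 2020 was dosed to the 2-year cap. Ethics approval time, or a new anticancer therapy, would shorten them. Table 10 was also revised in Amendment 2, and Amendment 5 updated the endocrinopathy guidance. The text of Table 10 before Amendment 5 is not available, so if the overlap is older, the exposure is longer by an unknown amount. No efficacy analysis changes.

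**What to change.** Reword the first endocrinopathy row of Table 10 to *Grades 1 and 2 (except Grade 2 adrenal insufficiency)*, and leave the specific row as it is. Notify sites that still have participants on treatment or in the 90-day immune-related follow-up.

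The cost is one table cell, made by clarification letter or in the next amendment. Intended management, data collection and analysis all stay the same.
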